## 1. SYNOPSIS

Title	Evaluation of the 5-year Safety and Performance of the Medtentia Annuloplasty Ring in Adults - Follow-up to Clinical Investigation 2010-040
Sponsor	Medtentia International Ltd Oy
Name of IMD	Medtentia Annuloplasty Ring (MAR)
Indication	Patients with mitral valve (MV) regurgitation requiring annuloplasty repair of their native MV with retention of the natural valve apparatus and normal valve orifice, remodeling of the annulus and prevention of secondary distension after valvuloplasties
Purpose of the Investigation	The purpose of this clinical investigation is to evaluate long-term safety and performance of the MAR in patients who underwent successful mitral valve surgery using Medtentia's MAR system in clinical investigation 2010-040 performed during June 2011 - April 2016
Design	Observational, single-center
Subject Population	11 subjects, who underwent MV repair operation with successful MAR implantation in clinical investigation 2010-040
Objectives	The primary objective of this clinical investigation is to evaluate long-term performance and safety of MAR five years after mitral valve repair surgery
Subject Selection	Inclusion Criteria  Subjects who participated in the clinical investigation 2010-040 and meet ALL of the following inclusion criteria are eligible for participation

	
in this investigation:
 
 
1. Signed Informed Consent Form
 
2. Subject had a successful MAR implantation in clinical investigation 2010-040
 
3. Subject is willing to participate in the follow-up study and to comply with the requirements of the CIP
 
 
Exclusion Criteria
 
Subjects who participated in the clinical investigation 2010-040 but had the MAR replaced with another MV repair ring or system are not eligible for participation in this investigation

Investigation Procedures	
Visit
 
After signing the Informed Consent Form, the subjects will have the following assessments:
 
 
• Demographics
 
• Relevant medical history after the last follow-up visit (2 years after MAR implantation) of investigation 2010-040
 
• Assessment for functional mitral regurgitation as defined by current American College of Cardiology/American Heart Association (ACC/AHA) guidelines
 
• Vital signs (pulse, blood pressure, and body temperature) and weight
 
• New York Heart Association (NYHA) rating
 
• Electrocardiography (ECG)
 
• Quality of Life Questionnaire (15D®)
 
• Trans-thoracic echocardiography (TTE)
 

Data Analysis and Statistics	
Definition of the analysis populations
 
Long-term follow up data of 11 subjects, who underwent MV repair operation with successful MAR implantation in clinical investigation 2010-040 performed during June 2011 - April 2016

	
Statistical methods
 
A statistical analysis plan (SAP) detailing the statistical analyses will be written and finalized prior to final data analyses
 
Qualitative and quantitative statistics will be used, as appropriate, to present and summarize the data collected in the clinical investigation

Endpoints	
Primary safety endpoints
 
The occurrence, nature and frequency of significant medical events since the last visit of clinical investigation 2010-040 as defined in section 8.4 of this Clinical Investigation Plan
 
Primary performance endpoints
 
Change in MR from the 2-year follow-up data point to the 5-year follow-up as measured by TTE. Success will be defined as no change or any improvement in MR class as described in the ACC/AHA Guidelines.
 
Secondary endpoints
 
Safety
 
 
• All-cause mortality collected retrospectively since the last visit of clinical investigation 2010-040
 
• The occurrence, nature and frequency of adverse device effects (ADEs) and/or device deficiencies (DDs) since the last visit of clinical investigation 2010-040
 
• Number of cardiovascular admissions occurred since the last visit of clinical investigation 2010-040
 
 
Other Safety
 
 
• The number of subjects with clinically significant abnormal findings in TTE, ECG, or vital signs and type of abnormal findings will be listed and tabulated
 

	
Performance
 
 
• Change from the clinical investigation 2010-040 2-year follow-up in the following MR parameters, as measured by TTE: 
 
- Left ventricle reverse remodeling (standard measurement points)
 
- Coaptation height
 
 
 
• Changes in NYHA classification when compared to the clinical investigation 2010-040 2-year follow-up visit.
 
• Number of subjects with recurrence of MR defined as changing of MR to moderate or severe according to ACC/AHA classification determined by TTE.
 
 
Other
 
 
• Number of subjects with re-operation or MV reintervention due MAR performance failure or malfunction
 
• Quality of life scores as measured by the 15D®questionnaire.
 

Data Collection	Data will be collected using Electronic Data Capture (EDC) system.
Investigation Duration	
The investigation duration for each individual subject includes only one visit. Subjects will undergo interview and assessments specified in this CIP
 
Estimated overall study duration from first subject first visit to last subject last visit May-June 2019

## 2. ABBREVIATIONS AND DEFINITIONS

Abbreviation	Definition
ACC	American College of Cardiology
ADE	Adverse device effect
AE	Adverse event
AHA	American Heart Association
ASADE	Anticipated serious adverse device effect
CE	Conformite Europenne (Conformity Mark for products marketed in the European Economic Area)
CI	Confidence interval
CIP	Clinical Investigation Plan
CRA	Clinical Research Associate
EC	Ethics Committee
ECHO	Echocardiography
ECG	Electrocardiography
eCRF	Electronic case report form
EDC	Electronic data capture
ERO	Effective regurgitant orifice area
ESC	European Society of Cardiology
GCP	Good Clinical Practice
IB	Investigator's Brochure
ICF	Informed Consent Form
ICH	International Conference on Harmonisation
ID	Identification
IMD	Investigational medical device
ISF	Investigator Site File
ISO	International Organization for Standardization
LV	Left ventricle
LVEF	Left ventricle ejection fraction
MAR	Medtentia Annuloplasty Ring
MEDDEV	Medical Device Directive
MedDRA	Medical Dictionary for Regulatory Authorities
MR	Mitral regurgitation
MV	Mitral valve
NYHA	New York Heart Association
RA	Regulatory authority
SADE	Serious adverse device effect
SAE	Serious adverse event
TTE	Trans-thoracic echocardiography

### 3. BACKGROUND AND RATIONALE

#### 3.1 Background Information

Mitral regurgitation (MR) is an abnormal flow of blood in the heart from the left ventricle back to the left atrium caused by an incomplete closure of the mitral valve (MV) (Cooper *et al.*, 1998). MR can result either from a structural or degenerative abnormality of the MV itself, or a distortion of the architecture or function of the left ventricle. With an estimated global prevalence of 1.7% and over 10% in people aged  $\geq 75$ , MR is the most common heart valve disease (Nkomo *et al.*, 2006; Mozaffarian *et al.*, 2016; Nishimura *et al.*, 2016).

Initially patients with MR may have no symptoms because of compensatory changes to the heart. If MR is left untreated, compensatory changes to the heart become irreversible (Nishimura *et al.*, 2016). The severity of MR usually worsens gradually, and severe MR eventually leads to left ventricular failure, various cardiac morbidities, and death if left untreated (Pozzoli *et al.*, 2016). 90% of patients with severe MR end up dying or requiring cardiac surgery within 10 years of diagnosis (Enriquez-Sarano *et al.*, 2009).

There are currently no generally accepted pharmacological treatments for MR. Surgery has been the only treatment truly improving patient outcomes, especially over the long term (Vahanian *et al.*, 2012). Therefore, the surgery is strongly recommended in the case of severe or moderate MR, as well as in asymptomatic patients in the case of progressive cardiac enlargement visible by ECHO (Falk *et al.*, 2017; lung *et al.*, 2002). Surgical intervention aims either at repairing the MV or at replacing it with an artificial valve (Nishimura *et al.*, 2016). Surgical MV repair, or MV annuloplasty, involves an annuloplasty ring that is implanted around the MV annulus, thus supporting the coaptation of the leaflets. Timely MV annuloplasty often associates with a good clinical outcome and normalized lifetime expectancy (De Bonis *et al.*, 2016; Pozzoli *et al.*, 2016). MV repair has been estimated to be clinically superior to valve replacement surgery and is therefore the preferred option (Jokinen *et al.*, 2007; Nishimura *et al.*, 2016; Pedrazzini *et al.*, 2010; Shang *et al.*, 2017; Zhou *et al.*, 2010).

The MV repair process, however, is both technically demanding and time-consuming: it usually requires careful placement of more than ten sutures, and experienced and multidisciplinary operators are required to obtain good outcomes (LaPar *et al.*, 2014; Nishimura *et al.*, 2016). The Medtentia Annuloplasty Ring (MAR) was designed to provide a simpler alternative for the current technically demanding mitral repair processes. In preclinical safety and efficacy studies conducted in sheep, the new MAR system has proven to be easy to use, well tolerated, and to have a functional outcome comparable to that of a certified annuloplasty ring. MAR was also

proven to effectively stop MR without causing thrombus formation or hemolysis (Jensen *et al.*, 2010; Konerding *et al.*, 2013). Furthermore, MAR rings were temporarily positioned in 18 patients undergoing otherwise conventional annuloplasty and then removed without incident before the annuloplasty continued (Medtentia International Ltd Oy, 2011). No safety issues were seen when annuloplasty using the MAR was performed in these studies.

During the years 2011-2014, MAR was implanted to 11 patients needing mitral valve regurgitation correction (investigation code: 2010-040) at two study stages. The outcomes of the study are presented in detail in the Clinical Investigation Report, dated 14-Feb-2019. As a conclusion this clinical investigation showed the first clinical evidence on MAR being an effective and well-tolerated method for the treatment of MR.

This follow-up study to evaluate the 5-year performance and safety of the MAR in the current subject population is expected to provide valuable insight into the longer-term performance and safety of the MAR.

### **3.2 Summary of Clinical Data Preceding the Follow-up Clinical Investigation (2010-040)**

The prospective, single-arm clinical investigation was conducted between 2011–2014 (clinical investigation code: 2010-040), which aimed at investigating the safety and performance of MAR in subjects with MR requiring mitral valve annuloplasty.

A total of 11 subjects with severe MR underwent successful mitral valve annuloplasty with MAR during two stages of this clinical investigation and were regularly followed up to 2 years after the surgery. At Stage 1 MAR Classic sizes available were 28-36 mm in 2 mm increments. At Stage 2, MAR Regular and Expanded sizes available were 26-40 mm diameters in 2 mm increments; Regular and Expanded corresponded to mitral leaflet's thicknesses.

During the first stage 17 subjects requiring mitral valve repair surgery were screened between June 2011 and August 2012. Implantation of the MAR was not attempted for one of these subjects, whose anterior leaflet was determined to be too large. MAR implantation was attempted but not completed for 9 subjects. Of these, three had thickened leaflets, two in addition to thick leaflets also had myxomatous mitral valve, one had annulus too small for the ring sizes defined in clinical investigation plan and available at that time, three had other anatomical features that made implantation unfeasible. Annuloplasty was completed using the MAR in the remaining 8 subjects, for one of these unsuccessfully leading to the replacement of MAR with a smaller Physio Ring. For one subject re-operation had to be done after few days due to continuous moderate-to-severe regurgitation and the MAR was replaced with a smaller Physio Ring. In total, the successful annuloplasty was completed using MAR (Classic) for 6

subjects during the Stage 1. As planned in the CIP, enrollment was then halted to allow a safety review by an independent data safety monitoring board (DSMB) composed of two clinicians with expertise in MV repair surgery and a biostatistician after the 6-month follow-up of the last of these subjects.

On 04-Feb-2013 DSMB reviewed the Stage 1 data and found no safety concerns thus concluding that it was ethical and feasible to continue the study as planned ([name] *et al.*, 2013).

As a consequence of the unexpectedly high number of patients with thickened leaflets, slight modifications were made to the ring design before the Stage 2 was opened for recruitment. A greater diversity of MAR sizes and an additional version of the MAR with a wider distance between the loops allowing implantation in patients with thicker mitral leaflets became available for Stage 2. Stage 2 started in July 2013, and the first implantation occurred on 10-Jul-2013. By May 2014, 5 subjects were successfully implanted with MAR and 2 were withdrawn due to anatomical anomalies. In August 2014 the project development was put on hold for a year. The company decided to terminate the study in September 2015 due to company's focus shift towards the development of a transcatheter technology for mitral regurgitation and strategical reasons. No new subjects were enrolled after June 2014.

Due to the limited number of subjects, the decision was made to use only descriptive statistics for data analysis.

MAR performance results showed that at the 3-month time point, MAR implantation had induced a 2-degree MR status improvement in 10 out of 11 subjects (90.9%; 95% CI 58.7–99.8%). Two years after surgery, MR status had improved by at least 2 degrees in all 11 subjects (100%; 95% CI 71.5–100). Improved score according to NYHA classification also confirmed that all subjects with MAR had benefited from the operation: all had normal mitral leaflet motion and diminished size of the left ventricle two years after the MAR implantation. Reverse remodeling of the left ventricle after MAR implantation led to recovery of the anatomical features of the MV in all subjects who underwent a successful surgery. Hence, after the two-year follow-up period defined by the 2010-040 study design, all MAR subjects had diminished left ventricle size. The improved MR result was further supported by the NYHA assessment of subjects' heart failure status that is based on an interview evaluating how much the potential heart condition limits the study subject's physical activity. Two years after MAR implantation, all subjects had reached class I functional classification and thus had no limitations of physical activity caused by their heart condition.

No deaths occurred in the hospital or during the 24-month follow-up. No device-related adverse events (ADEs) were detected in the subjects eligible for the study.

### **3.3 Risks and Anticipated Adverse Device Effects to Be Assessed**

This is an observational follow-up clinical investigation.

There were no adverse device effects (ADEs) nor serious ADEs (SADEs) in previous clinical investigation 2010-040.

## **4. INVESTIGATIONAL MEDICAL DEVICE INFORMATION**

Medtentia Annuloplasty Ring (Classic, Regular, and Expanded) and its accessories for selecting and implanting an appropriate mitral annuloplasty ring were used during the clinical investigation 2010-040.

The following disposition of investigational device type and ring sizes were during the clinical investigation 2010-040:

- At Stage 1 (year period 2011-2012), MAR Classic sizes were 28-36 mm in 2 mm increments.
- At Stage 2 (year period 2013-2016), MAR Regular and Expanded sizes were 26-40 mm diameters in 2 mm increments; Regular and Expanded corresponded to mitral leaflet's thicknesses.

Details on the device and its manufacturing process of the MAR can be found in the most recent Investigator's Brochure (IB) (Medtentia International Oy, 2019).

## **5. RISK EVALUATION**

### **5.1 Risks Associated with the Participation in the Clinical Investigation**

Medtentia International Ltd Oy does not foresee any risks associated with this investigation.

### **5.2 Risk/Benefit Assessment**

This is an observational follow-up clinical investigation. There are no additional risks anticipated, specific to participating in this study for the subjects. The investigation is not examining any experimental procedures and participation in the investigation is not predicted to affect the medical treatment received by enrolled subjects.

There is minimal potential for direct benefit to subjects as the investigation does not involve any change to their standard monitoring and treatment. However, there may be a benefit in the special attention paid to the subjects' cardiac function and picking up additional information from the subjects' assessment.

## **6. DESIGN OF THE CLINICAL INVESTIGATION**

### **6.1 Purpose**

This clinical investigation is a continuation of the clinical investigation 2010-040 aiming to assess the long-term outcomes of the surgical therapy of MR using MAR. The purpose of this clinical investigation is to evaluate 5-year safety and performance of the MAR in patients who underwent successful mitral valve surgery using Medtentia's MAR system in the clinical investigation 2010-040 performed during June 2011 - April 2016.

### **6.2 A description of the study design including justification based on clinical evaluation**

A pilot clinical investigation 2010-040 was conducted at the Helsinki University Central Hospital between June 2011 and April 2014. During two study stages of this clinical investigation MAR was implanted for 12 subjects. 11 of 24 consented subjects did not receive the device due to non-anatomical fit, mainly at Stage 1, therefore after sizing adjustment of the implant (Regular and Expanded) the enrolment rate improved significantly. For 1 subject MAR was replaced

before the operation was completed. For 1 subject the implantation was successful, but four days post-operation, MAR had to be replaced with another ring type due to the mismatch of the ring size. This emphasizes the importance of various ring sizes, as well as careful evaluation of patient's mitral valve anatomy before a MAR operation.

11 of 12 of the MAR population recovered from operation with improved mitral regurgitation and were regularly followed up to 2 years of ring implantation. The primary safety endpoints of the clinical investigation were met with no device-related safety issues and 100% survival. The primary performance endpoints were met with mitral regurgitation improvement of at least 2 degrees in mitral regurgitation class.

The limitations of clinical investigation 2010-040 include relatively small subject population, as well as the relatively short follow-up time for a surgical product. Therefore, an observational follow-up study to evaluate the 5-year performance and safety of the MAR in the current subject population was planned.

This follow-up study, 2010-040FU5, aims to include 11 MAR subjects for one follow-up visit in order to evaluate whether MAR has been able to keep the mitral regurgitation trivial or mild. Subjects are planned to enter this follow-up clinical investigation at least 5 years after MAR implantation.

The sponsor selected [REDACTED] hospital as a follow-up clinical investigation site based upon a site assessment considering appropriate facilities, qualifications of the investigators' experience with the intended procedures, and ability to conduct the study according to the clinical investigation plan.

### **6.3 Randomization and Blinding/Masking**

This section is not applicable.

### **6.4 Objectives and Endpoints**

#### **6.4.1 Primary Objectives**

##### **Safety**

- To evaluate the safety of the MAR in terms of longstanding complications and adverse events

##### **Performance**

- To evaluate the performance of the MAR 5 years post MV repair surgery

## **6.4.2 Secondary Objectives**

### **Safety**

- To evaluate the safety of the MAR in terms of survival since the last visit of clinical investigation 2010-040

### **Performance**

- To obtain additional performance information

## **6.4.3 Primary Endpoints**

### **Safety**

- The occurrence, nature and frequency of significant medical events since the last visit of clinical investigation 2010-040 as defined in section 8.4

### **Performance**

- Change in MR from the 2-year follow-up data point to the 5-year follow-up as measured by TTE. Success will be defined as no change or any improvement in MR class as described in the American College of Cardiology/ American Heart Association (ACC/AHA) Guidelines

## **6.4.4 Secondary Endpoints**

### **Safety**

- All-cause mortality collected retrospectively since the last visit of clinical investigation 2010-040
- The occurrence, nature and frequency of adverse device effects (ADEs) and/or device deficiencies (DDs) since the last visit of clinical investigation 2010-040
- Number of cardiovascular admissions occurred since the last visit of clinical investigation 2010-040

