# **8. STUDY PROCEDURES**

## **8.1 Informed Consent**

The subject may only be included in the follow-up study after providing written informed consent as described in Section 11.1 Informed Consent. Failure to obtain signed informed consent renders the patient ineligible for the study.

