### **8.3.1.2 *Medical history***

At the visit the subject's medical history will be documented including significant medical events, defined as events of cardiovascular origin and events fulfilling ADE and DD criteria, experienced since the last visit in the clinical investigation 2010-040.

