## 8.4 Adverse Events, Adverse Device Effects and Device Deficiencies

This is an observational follow-up study, consisting only of one visit. Significant medical events will be considered as events of cardiovascular origin and other events fulfilling, ADE and DD criteria. These events will be collected from the subject retrospectively from the timepoint of the last visit in the clinical investigation 2010-040.

It is of utmost importance that all staff involved in the investigation are familiar with the definitions and procedures and it is the responsibility of the Investigator to ensure this.

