### **8.4.1      Significant Medical Events**

Due to the nature and regulatory strategy of this investigation, the scope of adverse event reporting in this investigation has been limited to collection and reporting of the following significant medical events:

- Significant medical events according to the Table 1.
- Any Device Deficiency (DD) that might have led to a SAE if (a) suitable action had not been taken or b) intervention had not been made or c) if circumstances had been less fortunate. DD relates to inadequacy of an investigational medical device related to its identity,

quality, durability, reliability, safety or performance. This may include malfunctions, use error, or inadequacy in the information supplied by the manufacturer.

Regulatory authorities and EC will be informed about the retrospective events in the final report to be written in the end of this investigation.

The Investigator must record any of the events listed in the Table 1, regardless of relationship to the investigational medical device, and any DD that might have led to a SAE in the eCRF. Each unique event or diagnosis must be documented separately. Clearly related signs, symptoms and abnormal diagnostic procedure results should be grouped together and reported as a single diagnosis or syndrome whenever possible.

**Table 1. Significant medical events required to be collected and reported by the Investigator** (the list is based on standardized event reporting and data collection recommendations, Hicks et al. 2014 and 2017)

Event	Description
Death	

- Cardiovascular

- Non-cardiovascular

- Undetermined cause of death

Heart failure	Presentation of the patient for an urgent, unscheduled clinic/office/emergency department visit or hospital admission, with a primary diagnosis of heart failure
Myocardial infarction	
Hospitalization	For cardiovascular causes
Stroke or another cerebrovascular event	Should be assessed by a neurologist and CT/CMR imaging Severity should be documented: 

- Disabling

- Nondisabling

Percutaneous coronary intervention	It is defined as the placement of an angioplasty guidewire, balloon, or other device into a native coronary artery or CABG for the purpose of mechanical coronary revascularization  The assessment of coronary lesion severity by intravascular ultrasonography, coronary flow reserve, or fractional flow

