## **11. ADMINISTRATIVE PROCEDURES AND RESPONSIBILITIES**

### **11.1 Informed Consent**

Prior to enrollment to the clinical investigation, ICF will be given to each prospective subject, including an explanation of the investigation, duration, explanation of medical record access and patient anonymity, and specifies that data will be recorded, collected, processed and may be transferred (to either EEA countries and/or non-EEA countries). The ICF may be utilized if approved by the responsible EC. Adequate time will be allowed for the subject to consider participation in the clinical investigation. Any coercion or undue influence of potential subjects to participate must be avoided, and the subject's legal rights should not be waived. The subject will also be informed of his/her right to withdraw from the study at any time without giving a reason. If the subject is willing to participate in the investigation, both the subject and the Investigator or designated sub-Investigator who conducted the informed consent process must sign and date the ICF in accordance with local national requirements. The original signed ICF will be filed in the Investigator Site Files (ISF). The subject then will be given a copy of the signed ICF.

The ICF must be fully signed and dated prior to data collection or any other investigation-related activities required by the CIP. Failure to obtain signed informed consent renders the patient ineligible for the investigation

The ICF complies with the ISO 14155:2011 standard and is considered appropriate for this study will be submitted to the EC. The ICF will be in Finnish and will contain language that is non-technical and understandable to the subject. Any changes to the ICF suggested by the Investigator must be agreed by Medtentia International Ltd Oy before submission to the EC and a copy of the EC approved version must be provided to the CRA after EC approval.

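### All-cause mortality is an endpoint, but the only written way of collecting deaths runs through living, consenting attenders, and unknown vital status has no reporting rule

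*Protocol*

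**What the plan says.** **Endpoint.** Protocol 6.4.4 lists "All-cause mortality collected retrospectively since the last visit of clinical investigation 2010-040". It serves the survival objective in 6.4.2. Protocol 9.2.2.1 and SAP 4.5 (9.2.2.1) plan a frequency table for it, and confidence intervals, where appropriate, for safety data in the MAR population.

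**Death as a significant medical event.** Protocol 8.4.1 says "The Investigator must record any of the events listed in the Table 1, regardless of relationship to the investigational medical device". Death is the first row of Table 1, split into cardiovascular, non-cardiovascular and "Undetermined cause of death". The primary safety endpoint (6.4.3) points to section 8.4, so deaths feed it as well.

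**Collection route.** Section 8.3 gives one site visit. Section 8.3.1.2 has events documented at that visit as medical history. Section 8.4 states "These events will be collected from the subject retrospectively from the timepoint of the last visit in the clinical investigation 2010-040".

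**Consent.** Section 8.1: "Failure to obtain signed informed consent renders the patient ineligible for the study". Section 11.1: "The ICF must be fully signed and dated prior to data collection".

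**Population and enrolment.** Protocol 9.5 and SAP 4.1 define the MAR population by successful implantation, with no condition of consent or attendance. Protocol 6.7 and SAP section 3 let the number enrolled depend on who is found and agrees, with 11 as a ceiling. Protocol 6.10 and 9.7 expect all 11.

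**Missing data.** SAP 4.2 says only that nothing is imputed. Protocol 10.2 leaves the origin of source data to a separate form, which is not part of these documents.

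**The concern.** An interview after signed consent cannot record a death that has already occurred. The route therefore yields zero deaths before the visit whatever the true number. Protocol 3.2 reports no deaths through 24 months, so any death in this cohort falls in the window this study is meant to cover.

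A reader of the final report could not tell whether no deaths means that none of the 11 died or that nobody checked those who did not come. Any error runs one way, because missed deaths can only make mortality look lower. The re-operation endpoint (protocol 6.4.4, SAP 9.2.2.4) has the same gap for anyone who does not attend.

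**Working it through.** **Step 1: follow the written route for a subject who died after the 2-year visit.**

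| Requirement | Where | Can it be met? |
|---|---|---|
| Death is recorded and mortality tabulated | Protocol 6.4.4, 8.4.1; SAP 4.5 | Required |
| Consent form signed before data collection | Protocol 11.1 | No |
| Event obtained from the subject | Protocol 8.4 | No |
| Documented at the single visit | Protocol 8.3, 8.3.1.2 | No |
| Counted in the MAR population | Protocol 9.5; SAP 4.1 | Yes, by implantation |

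A living subject who declines or cannot be found also stays in the MAR population, with vital status unknown.

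**Step 2: look for another route.** Protocol 11.1 mentions access to medical records, but as something the consent form explains, so it reaches people who sign. The word retrospectively in the endpoint gives a direction in time and no source. The form cited in protocol 10.2 might name one, but it cannot be inspected. Neither document mentions a registry, a hospital-record check for non-participants, or an exception to consent for this purpose.

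**Step 3: reproduce the plan's own intervals to fix the method.** Protocol 3.2 gives 10/11 as 58.7–99.8% and 11/11 as 71.5–100%. Exact (Clopper–Pearson) limits match both:

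- 11/11, lower limit: 0.025^(1/11) = 0.715.
- 10/11: lower limit is the 2.5% quantile of Beta(10, 2) = 0.587; upper limit is 0.975^(1/11) = 0.998.

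Wilson intervals do not match (62.3–98.4% and 74.1–100%), so the exact method is used below.

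**Step 4: bound the effect.** Let k be the number of the 11 whose vital status is not ascertained. The documents do not give k, so 0 to 3 is an assumed range. With no deaths among n subjects, the exact upper limit is 1 − 0.025^(1/n). Neither document fixes the denominator of the mortality table, so both forms are considered. If non-attenders stayed in the denominator without an event, the table would read 0/11 (0–28.5%) for every k.

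| k | Attenders only (exact 95% CI) | Highest possible cohort mortality (exact 95% CI) |
|---|---|---|
| 0 | 0/11 (0–28.5%) | 0/11 (0–28.5%) |
| 1 | 0/10 (0–30.8%) | 1/11 = 9.1% (0.2–41.3%) |
| 2 | 0/9 (0–33.6%) | 2/11 = 18.2% (2.3–51.8%) |
| 3 | 0/8 (0–36.9%) | 3/11 = 27.3% (6.0–61.0%) |

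The lowest possible cohort mortality is 0/11 in every row, so the undetermined range is k × 1/11, or 9.1 percentage points per subject. The reported estimate is zero with either denominator. The confidence interval does not cover this uncertainty, because it describes sampling error among subjects whose status is known.

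**The case against.** **No rule scores non-attenders as alive.** A reader might infer that the report will show 0/11 with absent subjects counted as survivors. The documents do not say so, and SAP 4.2 points the other way, since counting an unknown as no death would be a form of imputation. This stands against any claim that 0/11 will be reported. It does not remove the gap, because an attenders-only table is still a survivor sample.

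**A death may come to light anyway.** Former subjects are to be contacted and invited (protocol 6.7; SAP section 3), which could reveal a death, and a disposition summary is planned (protocol 9.6; SAP 4.3), which should show any shortfall from 11. It would therefore be too strong to say that a death will go unnoticed. But nothing says that a death learned of in this way enters the endpoint, and the disposition categories are not given.

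**The consent text can be read narrowly.** Section 8.1 governs inclusion, and section 11.1 opens with prospective subjects. Neither expressly forbids a status check on someone not enrolled, and the mortality endpoint could be read as a specific provision beside the general rules. That is fair: the documents do not prove that a records check is prohibited. They provide none, however, and 11.1 ties data collection to a signature without exception.

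**Two further readings do not hold.**

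- Section 8.4 describes the events as "Significant medical events will be considered as events of cardiovascular origin and other events fulfilling, ADE and DD criteria", and 8.3.1.2 is similar, which might suggest that non-cardiovascular deaths are lost. Table 1 lies inside 8.4 and is the operative reporting rule, and all-cause mortality is a separate endpoint, so this wording loses no death.
- The ring-replacement exclusion (7.1) has no time limit and might seem to remove a late replacement from the re-operation count. It limits participation, not the MAR population, and was probably written for the replacements during 2010-040 (3.2, 6.2).

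Both are drafting clarifications only.

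**Conclusion.** The point holds with moderate confidence and should be fixed. As written, the collection route gives a survivor-only mortality result for a population defined by implantation, with no vital-status source for the rest and no rule for showing unknown status.

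The size depends on attendance. It is nil if all 11 attend. Otherwise up to 9.1 percentage points of cohort mortality are undetermined for each subject not ascertained. The scenarios of one to three such subjects and the 0/11 denominator are assumptions. The documents give no mortality rate, so nothing is claimed about how likely a death is. The study is descriptive (protocol 9.1), so no test is affected; what is at stake is the meaning of a reported zero. Confidence is moderate because the source-data form may name a source and because the consent text is partly open to interpretation.

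**What to change.** **Protocol.** State that vital status, date and cause of death, and mitral valve re-operation since the 2-year visit are ascertained for all 11 MAR subjects from named records sources, whether or not they attend, subject to ethics approval. Reconcile 8.3.1.2, 8.4 and 11.1 with this. In the same edit, align the event definition in 8.3.1.2 and 8.4 with Table 1, and clarify the period that the ring-replacement exclusion covers.

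**SAP 4.5 and 9.2.2.4.** Report dead, alive and unknown out of 11, and re-operated, not re-operated and unknown out of 11. In the disposition table planned in SAP 4.3, give the counts deceased, not located, declined and attended. If records access is not approved, state that mortality among non-attenders is unknown and do not report it as zero.

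**Cost.** A protocol amendment with ethics approval (11.3), a few lines in the SAP and a records check on at most 11 people. The reported rates may be less favourable. Visits were planned for May–June 2019 and the SAP is dated 27 February 2020. If visits are complete, the SAP changes and an ethics-approved records check are the workable part.
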